Abbreviations: C=cycle, D=day, ECG=electrocardiogram, EOT=end of treatment, HAT=hereditary alpha tryptasemia, PGx=pharmacogenomics, PK=pharmacokinetics.

Sample collections will be performed prior to dosing with study drug and, as applicable, prior to ECG for scheduled visits involving study drug administration and/or ECGs, unless otherwise noted. All samples will be sent to the central laboratory. Refer to the Laboratory Manual for details.

- (a) After 15 cycles, blood sample collections will be performed on Day 1 of every odd-numbered cycle (eg, C17D1, C19D1) and as clinically indicated.
- (b) Should be collected prior to the first dose of study drug if possible (at Screening), but may be collected at any time during the study.
- (c) The buccal swab for tryptase alpha/beta 1 (*TPSAB1*) genetic testing of HAT should be collected prior to the first dose of study drug if possible (at Screening), but may be collected at any time during the study. Subjects should be instructed to refrain from eating or drinking for 60 minutes prior to the buccal swab.
- (d) Postdose blood samples for PK at C1D1 and C2D1 will be collected for subjects in Part 1 and Part 2 Stage 1 (but not for subjects in Part 2 Stage 2).

Table 3: Schedule of Response Assessments

	Screening	Cycle 3	Cycle 6	Cycle 9	Even-Numbered Cycles (C12 + beyond) (a)	EOT
Study Day	-42 to -1	1	1	1	1	
BM sample for mutational analysis including myeloid mutation panel (b)	X	X	X	X	X	X
BM biopsy (or extracutaneous biopsy) for eligibility and response assessments (c)	X	X	X	X	X	X
Radiological evaluations (d) -MRI/CT abdomen/pelvis -Skeletal imaging (as appropriate)	X	X	X	X	X	X
Spleen palpation (e)	X	X	X	X	X	X
Photography (f)	X	X	X	X	X	X
Overall response assessment (g)		X	X	X	X	X

Abbreviations: BM=bone marrow, C=cycle, CI=clinical improvement, CR=complete response, CRh=CR with incomplete hematologic recovery, CT=computed tomography, D=day, ECG=electrocardiogram, EOT=end of treatment, IWG-MRT-ECNM=International Working Group-Myeloproliferative Neoplasms Research and Treatment European Competence Network on Mastocytosis, MRI=magnetic resonance imaging, PR=partial response.

Sample collections will be performed prior to dosing with study drug and, as applicable, prior to ECG for scheduled visits involving study drug administration and/or ECGs, unless otherwise noted. All samples will be sent to the central laboratory. Refer to the Laboratory Manual for details.

- (a) After 12 cycles, assessments will be performed every 6 cycles (eg, C18D1, C24D1, etc) and as clinically indicated.
- (b) Additional exploratory analyses may be performed on BM samples to further explore pharmacodynamic markers in subjects with AdvSM.
- (c) BM samples will be obtained per local standard of care at Screening, C3D1, every 3 cycles from Cycle 6 until Cycle 12 (D1 of C6, C9, C12), every 6 cycles after Cycle 12 (D1 of C18, C24, etc), and at EOT if a sample has not been obtained within 7 days. Bone marrow samples will be sent for routine pathology, cytogenetics, flow cytometry, and molecular analysis including assessment of *KIT* mutation status (eg, D816V). If an initial response (CR, CRh, PR, or CI) is achieved on or after C12, a repeat BM assessment will be performed 12 weeks after the initial documented response to confirm response per modified IWG-MRT-ECNM response criteria. BM samples (including those from unscheduled visits) will be sent for analysis at a central laboratory. For subjects who meet WHO diagnostic criteria for SM based on the presence of mast cell aggregates in extracutaneous organs rather than BM, biopsy of the extracutaneous organ should follow the same response assessment schedule.
- (d) Imaging will be performed every 3 cycles beginning at C3D1 (C6, C9, C12), and then every 6 cycles thereafter (C18, C24, etc) thereafter and as clinically indicated. If an initial response (CR, CRh, PR, or CI) is achieved on or after C12, a repeat scan will be performed 12 weeks after the initial documented response to confirm response per modified IWG-MRT-ECNM response criteria. Liver and spleen size and volume will be measured by MRI to assess hepatomegaly and splenomegaly, respectively. A CT scan may be used if MRI cannot be performed. The same method of evaluation should be followed

- from baseline. Skeletal imaging is required at Screening for all subjects to assess for baseline lytic lesions and/or pathologic fractures. Changes in the size of bony lesions will be assessed with skeletal imaging.
- (e) Assessment of the spleen by palpation is required at Screening and response timepoints to confirm response per modified IWG-MRT-ECNM response criteria.
 - (f) Photography assessments for skin or other clinically relevant lesions will be repeated every 3 cycles (as applicable) if skin lesions are present at Screening or develop during the treatment period, per Investigator discretion. After 12 cycles, photography assessments will be performed every 6 cycles and as clinically indicated.
 - (g) Overall response assessment will be performed at C3D1, and every 3 cycles thereafter beginning at C6D1 (C6, C9, C12), and then every 6 cycles (C18, C24, etc) thereafter and as clinically indicated and during the 12-week confirmation of response, as applicable. If an initial response (CR, CRh, PR, or CI) is achieved on or after C12, an overall response assessment will be performed 12 weeks after the initial documented response to confirm response per modified IWG-MRT-ECNM response criteria.

SPECIAL CONSIDERATION FOR THE USE OF REMOTE VISITS

When necessary and appropriate, investigative sites may use telemedicine visits, using adequate audio and video equipment, to interact with subjects to make health assessments in the home for the purpose of augmenting care, assessing emerging or existing adverse events, adjusting concomitant medications, or arranging for study-related local laboratory assessments.

If needed, due to subject/site circumstances such as COVID-19, study safety laboratory assessments may be obtained at a laboratory closer to the subject's home per the discretion of the treating physician and with approval from the Sponsor. The laboratory assessments should be reviewed, and appropriate follow-up should be completed per protocol and standard of care. The normal limits for laboratory findings for such laboratory assessments should be included in the subject's health records and recorded on the appropriate electronic case report form (eCRF). If alternative laboratories are used frequently, additional paperwork may be required for the study files and databases in accordance with regulations. Please discuss with the Medical Monitor and/or Sponsor.

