Study Title: A Phase 2 Open-Label, Multicenter Clinical Study of the Safety, Efficacy, Pharmacokinetic, and Pharmacodynamic Profiles of CGT9486 as a Single Agent in Patients With Advanced Systemic Mastocytosis		
Protocol Identifier: CGT9486-20-201 NCT: NCT04996875 EudraCT: 2021-001010-10		
Phase of Development: 2		
Study Center(s): Approximately 55 centers in North America, Europe, and other international locations		
Study Duration: The total duration of the study is expected to be approximately 7 years. Screening Period: Up to 42 days Treatment Period: From the initiation of therapy through the End of Treatment Visit following the last cycle of bezuclastinib. Subjects will continue to receive treatment with bezuclastinib until disease progression, intolerable toxicity, Investigator decision, withdrawal of consent, or other protocol-specified reason for discontinuation of study drug. Long-term Follow-up Period: Subjects will be followed for at least 2 years following discontinuation of study drug to assess survival. The study will continue until all subjects have completed at least 2 years of follow up for overall survival, withdrawn from study participation, been lost to follow-up, or died, whichever occurs first.		
Number of Subjects (planned): The total number of planned subjects with advanced systemic mastocytosis (AdvSM) enrolled in the study is up to approximately 120 and includes: Part 1: Dose Optimization will enroll approximately 28 subjects, including up to 4 subjects who are non-evaluable based on the modified International Working Group-Myeloproliferative Neoplasms Research and Treatment European Competence Network on Mastocytosis (IWG-MRT-ECNM) response criteria Part 2: Expansion will enroll approximately 75 subjects who are evaluable based on the modified IWG-MRT-ECNM response criteria, and up to approximately 15 additional subjects who are non-evaluable based on the modified IWG-MRT-ECNM response criteria		
Objectives and Endpoints:		
	Objectives	Endpoints
Part 1: Dose Optimization		
Primary	To identify a clinically active and tolerable systemic	
 Safety assessments (incidence of adverse events [AEs], serious adverse events [SAEs], changes

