Radiological Evaluations - MRI/CT abdomen/pelvis - Skeletal imaging (as appropriate)	Refer to Table 3 Schedule of Response Assessments.																					
Spleen palpation	Refer to Table 3 Schedule of Response Assessments.																					
QOL assessments (m)		X							X				X				X		X			
MAS (n)	X							X				X		X				X	X			
Bezuclastinib administration (o)	Daily through Cycle (a)																					
Study drug diary (p)		X							X				X (a)		X (a)		X (a)					
Overall response assessment	Refer to Table 3 Schedule of Response Assessments																					
AE monitoring (q)	X	X																				

Table 1: Schedule of Assessments and Procedures

	Screening	Cycle 1							Cycle 2				Cycles 3-15 (a, b)		Even-Numbered Cycles (C16+ beyond) (a, b)		Odd-Numbered Cycles (C17+ beyond) (a, b)		EOT (c)	SFU	Long-Term Follow-Up
Study Day	-42 to -1	1	2	4*	8	11*	15	22	1	8*	15	22*	1	22	1	22	1	22		30 d after last dose	Every 3 months after SFU
Window (Days)				±1	±2	±1	±2	±2	±2	±2	±2	±2	±3	±3	±3	±3	±3	±3		±7	±7
Concomitant medications (q)	X	X																			
Survival status (r)																					X
Disease status (s)																					X

Abbreviations: AE=adverse event, C=Cycle, CT=computed tomography, D/d=day, ECG=electrocardiogram, ECOG=Eastern Cooperative Oncology Group, eCRF=electronic case report form, EOT=end of treatment, HCV=hepatitis C virus, ICF=informed consent form, IWG-MRT-ECNM=International Working Group-Myeloproliferative Neoplasms Research and Treatment European Competence Network on Mastocytosis, MAS=Mastocytosis Activity Score, MRI=magnetic resonance imaging, PBS=peripheral blood smear, PE=physical examination, PK=pharmacokinetic, QOL=quality of life, SAE=serious adverse event, SFU=Safety Follow-up, TEAE=treatment-emergent adverse event.

One cycle = 28 days.

Standard of care assessments or procedures that may confirm study eligibility requirements may be performed prior to a subject signing the ICF.

On-treatment assessments and sample collections will be performed prior to dosing with study drug and, as applicable, prior to ECG for scheduled visits involving study drug administration and/or ECGs, unless otherwise noted. Additional assessments to evaluate subject safety and efficacy may be performed at unscheduled visits and will be recorded in the eCRFs.

* Additional hematology and chemistry assessments to be performed for subjects in Part 1 and Part 2 Stage 1 only.

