(a) After 15 cycles, dispensation of study drug for at-home administration and study drug diary will be adjusted accordingly.

(b) At C15 and beyond, and at most other study visits, clinical chemistry, hematology, pregnancy testing (women of childbearing potential only), AE monitoring, and collection of concomitant medications will be performed.

(c) EOT assessments should be performed within 7 days of decision to permanently discontinue study treatment.

(d) Subjects should be dosed as soon as possible after randomization and preferably within 7 days before receiving their first dose on C1D1.

(e) A complete PE will be performed at Screening only. At all other study visits, a targeted PE will be performed based on Investigator’s judgment and careful evaluation of the subject’s signs and symptoms.

- (f) Height at Screening only.
- (g) A single 12-lead ECG will be performed after the subject has been resting in supine or semi-supine position for at least 5 minutes. At all predose and postdose intervals, each ECG should occur just prior to each PK blood sample collection.
- (h) On C1D1 and C2D1, a single ECG will be performed predose (within 30 min prior to dosing) and at 1 (\pm 5 minutes), 3 (\pm 15 minutes), 5 (\pm 15 minutes), and 8 (\pm 30 minutes) hours postdose.
- (i) Safety laboratory tests (hematology, chemistry) may be completed 1 day prior to the visit on C1D1 (after randomization) or on C2D1.
- (j) Serum tryptase will be collected as indicated and at all response time points. Serum tryptase will be tested locally. A blood sample will also be collected and tested at a central laboratory. Additional exploratory analyses may be performed on blood samples to further explore pharmacodynamic markers in subjects with AdvSM.
- (k) Subjects with a positive HCV antibody may be eligible if HCV RNA is undetectable on a quantitative HCV RNA assay, following discussion with the Medical Monitor.
- (l) Women of childbearing potential only. A serum pregnancy test (β -human chorionic gonadotropin) will be performed at Screening, and a urine pregnancy test will be performed at subsequent visits.
- (m) QOL assessments to include Patient Global Impression of Severity (PGIS), Patient Global Impression of Change (PGIC), and the Mastocytosis Quality of Life Questionnaire (MC-QoL). PGIC will be performed starting on C2D1.

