- (n) The MAS will be completed where appropriate translations are available at Screening on D -42 (\pm 5 days) through D -35 (\pm 5 days). Thereafter, the MAS will be completed on Days 22-28 of each 28-day cycle through C15 and on Days 22-28 of odd-numbered cycles at C17 and beyond. The MAS must be completed at EOT and continuing for 7 days total unless an MAS was completed within the previous 14 days. The time window for starting the MAS is \pm 2 days.
- (o) Study drug bezuclastinib will be dispensed to the subject on Day 1 of each cycle for daily at-home administration. Treatment will be continuous; there will be no gaps between cycles. On days of a scheduled clinic visit, study drug will be administered at the clinic after visit procedures and assessments are performed.
- (p) A Study Drug Diary will be dispensed to the subject at the start of each cycle. Beginning at Cycle 15, subjects will be provided with diaries for use over 2 cycles. Subjects bring their diary with them to each study visit. Diary information will be reviewed and/or collected by the site during study visits.
- (q) From the signing of the ICF until the start of study treatment (C1D1), only SAEs or AEs related to on-protocol procedures will be collected. TEAEs will be collected from the start of study treatment until 30 days after the last dose of study drug. All medications will be recorded at Screening and collected through 30 days after the last dose of bezuclastinib. Any SAEs considered to have at least a possible relationship to the study drug and discovered by the Investigator at any time period after EOT should be reported.
- (r) Survival follow-up may be done via phone (with subject or referring physician).
- (s) Includes the recording of new anticancer therapy (therapy type, start and stop dates, and response to treatment).

Table 2: Schedule of Pharmacokinetics, Pharmacodynamics, and Biomarker Assessments

		Screening	Cycle 1			Cycle 2			Cycles 3-15 (a)	Odd-Numbered Cycles (C17 + beyond) (a)	EOT
Study Day		-42 to -1	1	2	15	1	2	15	1	1	
Blood sample for PGx (b)		X (b)									
Buccal swab for TPSAB1 gene (HAT) (c)		X (c)									
Blood sample for bezuclastinib PK	Predose: -30 min		X	X	X	X	X	X	X	X	
	Postdose: 1 h (± 5 min), 3 h (± 15 min), 5 h (± 15 min), 8 h (± 30 min)		X (d)			X (d)					
	Any time during Study Visit										X

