NOTE: Oral antibiotics for a controlled infection are permitted with Medical Monitor approval. Patients on antimicrobial, antifungal, or antiviral prophylaxis are not specifically excluded if all other inclusion/exclusion criteria are met.
8. History of clinically significant bleeding event within 30 days before the first dose of study drug or need for therapeutic anticoagulation on study.
9. Diagnosed with or treated for malignancy other than the disease under study within the prior 3 years before enrollment or expected to need treatment for an active malignancy. (The following are allowed within 3 years of study enrollment if the subject has received definitive local therapy [eg, surgical excision, external beam radiation, or other local therapy with curative intent]: non-melanoma skin cancers, localized prostate cancer, or carcinoma in situ.)
10. Any condition that could hamper compliance with the study protocol in the judgment of the Investigator.
11. Pregnant or currently breastfeeding.
12. Received any cytoreductive therapy (including midostaurin and other tyrosine kinase inhibitors, hydroxyurea, azacitidine) or any investigational agent less than 14 days, and for cladribine, interferon alpha, pegylated interferon, and any antibody therapy (eg, brentuximab vedotin) less than 28 days, before obtaining screening bone marrow biopsy for this study.
13. Received hematopoietic growth factor (eg, granulocyte colony-stimulating factor [G-CSF], granulocyte-macrophage colony-stimulating factor) support within 14 days before the first dose of study drug.
14. Received strong CYP3A4 inhibitors or inducers within 14 days or 5 drug half-lives, whichever is longer, before the first dose of study drug or the need to continue treatment with strong CYP3A4 inhibitors or inducers during the study (Refer to [Appendix H](#)).
15. Need for treatment with steroids (>10 mg prednisone or equivalent per day). Subjects on a stable dose of prednisone or equivalent that is ≤10 mg per day are eligible.
16. Known hypersensitivity to bezuclastinib or any of its components.

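### The only scheduled pre-dose MAS ends at least 30 days before first dose, can open before screening does, and cannot be completed on schedule when screening is short

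*Protocol*

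**What the plan says.** The Synopsis allows screening to last at most six weeks ("Screening Period: Up to 42 days"), and Table 1 labels the screening column D -42 to D -1. No minimum length is given. Footnote (d) to Table 1 encourages prompt dosing: "Subjects should be dosed as soon as possible after randomization and preferably within 7 days before receiving their first dose on C1D1".

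Table 1 marks one MAS before dosing, at Screening. Footnote (n) sets its timing: "The MAS will be completed where appropriate translations are available at Screening on D -42", then, after a ± sign, "5 days) through D -35", which itself carries ±5 days. The next MAS comes after a full three weeks of treatment: "Thereafter, the MAS will be completed on Days 22-28 of each 28-day cycle through C15". The same footnote closes with a different tolerance: "The time window for starting the MAS is" ±2 days. Appendix I (AI-4) describes the MAS as a daily evening diary kept on 7 consecutive days.

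Section 2 lists MAS change and percent change from baseline among the secondary endpoints, and Section 8.8 summarises them by part, stage and dose cohort. The other patient-reported scales (PGIS and MC-QoL) are first collected on Cycle 1 Day 1 according to Table 1.

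Exclusion criterion 12 in Section 4.2 requires prior cytoreductive therapy to have stopped 14 days, or 28 days for some agents, "before obtaining screening bone marrow biopsy for this study". The interval is counted from the marrow, not from the MAS or the first dose. Table 3 allows the screening marrow on any day from D -42 to D -1.

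**The concern.** A baseline for a change score should describe the subject just before treatment. Here it is tied to the far end of screening. Whatever happens to symptoms between the diary and the first dose enters the change score, including any effect of stopping earlier therapy. No untreated arm could separate that from a drug effect: Part 1 and Part 2 Stage 1 randomize between bezuclastinib doses, and Stage 2 is single-arm.

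The schedule also works against itself. The quicker a subject is screened and dosed, the less likely a full diary can be completed in its window. Day -42 is counted back from a first-dose date that the site cannot yet know, because Section 6.3 makes enrollment wait for all screening assessments and Eligibility Committee approval.

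A statistical analysis plan can choose among the pre-dose values that exist. It cannot supply a later one if the protocol does not schedule it.

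**Working it through.** The plan gives no figure to reproduce; the check is day arithmetic.

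**Inputs**
- MAS start D -42 ±5, end D -35 ±5; later start tolerance ±2 (Table 1, footnote n).
- Screening D -42 to D -1 (Table 1).
- Diary length 7 consecutive days (AI-4).
- Washout 14 or 28 days before the screening marrow (Section 4.2, criterion 12).
- Consent before any study-specific assessment (Section 6.1).

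**Placement of the baseline**
- Earliest: -42 - 5 = D -47 to -35 - 5 = D -40, or 6.7 to 5.7 weeks before dosing.
- Nominal: D -42 to D -35, or 6.0 to 5.0 weeks.
- Latest: -42 + 5 = D -37 to -35 + 5 = D -30, or 5.3 to 4.3 weeks.
- Permitted days: D -47 to D -30, which is 47 - 30 + 1 = 18 days. Those before screening opens are D -47 to D -43, which is 5 of 18.
- Nominal span: 42 - 35 + 1 = 8 days, for a 7-day diary.
- With ±2 instead of ±5, the start would run from D -44 to D -40. The two tolerances conflict unless ±2 is meant only for later visits, which the footnote does not say.

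**Short screening.** If consent is signed on D -L, with L from 30 to 42, the permitted diary days left are D -L to D -30, or L - 29 days.

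| Screening length L (days) | Permitted MAS days left | Full 7-day diary? |
|---|---|---|
| 42 | 13 | yes |
| 37 | 8 | yes |
| 36 | 7 | yes |
| 35 | 6 | no |
| 30 | 1 | no |
| 28 or fewer | 0 | no |

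Seven days need L - 29 ≥ 7, so L ≥ 36. Starting within the stated start window is slightly stricter: the latest start is D -37, so L ≥ 37.

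**Overlap with prior therapy.** For a marrow on day B and a washout of w days, the last allowed prior dose is on day B - w.
- It reaches the nominal MAS week if B - w ≥ -42, so B ≥ w - 42. For w = 14 this is D -28 or later; for w = 28, D -14 or later.
- It can cover the whole nominal week if B - w ≥ -35, so B ≥ w - 35. For w = 14 this is D -21 or later; for w = 28, D -7 or later.
- With a marrow on D -42, the last prior dose is no later than D -56 or D -70, so there is no overlap.

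**The case against.** The strongest reply is that this matters little. MAS is one of several patient-reported measures, is collected only where a translation exists, and is summarised without a hypothesis test. Section 8.2 rests dose decisions on safety, biomarker, clinical efficacy and PK endpoints. All of that stands, and it limits the weight of the point.

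A reader might infer that subjects with short screening have no valid baseline. The protocol does not support that. Nothing in it voids a 7-day MAS completed before first dose but outside the window; such a value is off schedule, yet still pre-treatment. Nor does it show that short screening is common, since marrow, imaging, central pathology review and committee approval all take time.

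A reader might also infer that the baseline is generally contaminated by prior therapy. Overlap arises only with later marrows, and the protocol gives no distribution of marrow dates, no share of pre-treated subjects and no direction of bias.

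The contrast with PGIS and MC-QoL should not be read as 30 to 47 days against zero. Those scales are collected on Cycle 1 Day 1 but look back one and two weeks respectively (Appendix I). A gap in timing remains, but a smaller one than the collection dates suggest.

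The days before D -42 are mainly a drafting matter, because consent must come first. What the reply does not answer is that the only scheduled baseline ends a month or more before dosing.

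**Conclusion.** The schedule in footnote (n) is poorly fixed and inconsistent with the screening period. On any permitted placement the baseline MAS ends at least about 30 days before first dose; 5 of its 18 permitted days lie before screening opens; and screening of fewer than about 36 days leaves a baseline that is incomplete, missing or off schedule. Overlap with prior cytoreductive therapy is possible with a late marrow (from D -28 under the 14-day rule, from D -14 under the 28-day rule), but its frequency and effect cannot be estimated from the protocol.

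The consequence is limited to interpreting MAS change and percent change from baseline, a descriptive secondary endpoint. The primary response-rate analysis does not use MAS and is unaffected. The conclusion assumes that study days are counted back from Cycle 1 Day 1 and that screening starts at consent.

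**What to change.** **Subjects not yet dosed.** Collect the 7-day MAS within screening as close as practicable to Cycle 1 Day 1, for example on the last 7 consecutive days before first dose, with a window that fits the interval from randomization to dosing. A diary on D -7 to D -1 would also fall after the last prior cytoreductive dose: a marrow no later than D -1 puts that dose no later than D -15 (14-day rule) or D -29 (28-day rule), assuming none is given after the marrow. In the same edit, reconcile the ±5-day and ±2-day tolerances and the 8-day span with the 7-day instrument.

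**Subjects already dosed.** Keep the MAS collected, accept any off-schedule MAS completed before first dose, and show MAS change by baseline-to-dose interval. Choosing the last pre-dose MAS would mostly return the same early value, so this describes the problem rather than removing it.

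**Cost.** A footnote and diary-schedule change. The data will hold two baseline timings, which the table by interval makes visible. The first-dose date must be known about a week ahead, which pulls against dosing as soon as possible after randomization. Part of the diary may be completed after the open-label dose is known, which could colour the answers.
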